## **2.3 Analysis Periods**

On-Treatment Period: This analysis period includes all data from the first dose of study drug to 2 days after the last dose of the study drug administration (inclusive).

Up-to-End-of-Treatment Period: This analysis period includes all data from first dose to end of treatment visit (i.e., last efficacy-evaluation date - Month 12 or ESMD visit)

Up-to-Last-FU (last contact): This analysis period includes all data from first dose to trial reference end date.

## **2.4 Definition of Subgroups**

Descriptive summaries of efficacy and safety may be done by considering the following subgroups:

- Age groups
- Sex
- Race
- Ethnicity
- Geographic region
- Baseline Creatinine Clearance (CrCl)
- Weight groups
- Type of antiplatelet/anticoagulant therapy prior to enrollment
- Others (e.g., use of central venous lines for > x days, and other parameters related to baseline characteristics of Fontan population – to be specified in the DPS)

## **3. SUBJECT INFORMATION**

Summary statistics (arithmetic mean, standard deviation, median, minimum and maximum for quantitative variables) will be presented by treatment. Frequency tables for qualitative data will be provided. No statistical tests will be performed to compare these characteristics across treatment groups. Unless stated otherwise, all subject information summaries will be based on safety analysis set and will be presented for rivaroxaban combined from Parts A and B, ASA and rivaroxaban from Part B, and rivaroxaban from Part A.

### **3.1 Enrollment and Medical History**

Enrollment, screen failures, and inclusion/exclusion criteria will be summarized for all screened subjects.

Medical history findings will be summarized using Medical Dictionary for Regulatory Activities (MedDRA) by Primary System Organ Class / High Level Term.

Type and other relevant information of the Fontan procedure performed will be summarized (details specified in the DPS).

### **3.2 Demographics and Baseline Characteristics**

Descriptive statistics by treatment group will be provided for the baseline demographics and disease characteristics.

### **3.3 Disposition Information**

The number of subjects and the reasons for premature discontinuation of study treatment will be summarized by treatment group as recorded on the eCRF.

The distribution of time from enrollment into the study to early discontinuation will be shown by KM plot.

A subject will be considered to have completed the study if the subject completes:

- The Follow-Up Contact 30 days after the last dose of study drug taken for subjects who complete the 12 month treatment
- The ESMD Month 12 Follow-Up for subjects who discontinue the study drug prematurely

Available vital status at the planned treatment end period (Month 12) will be summarized for subjects who prematurely discontinued the study or were lost to follow up.

### **3.4 Treatment Compliance**

Rivaroxaban will be administered twice daily in an open-label fashion. Rivaroxaban will be taken in the morning and in the evening (approximately 12 hours apart) as described in study booklet.

Subjects randomized to ASA will receive approximately 5 mg/kg as a single dose. ASA will be provided as tablets according to the local practices.

Dose adjustments due to increased body weight will be made at Month 6 for subjects in Parts A and B for both rivaroxaban and ASA.

IWRS will keep track of study drug dispensed to subjects in both Part A and Part B. Study drug accountability will be performed at each visit.

For each subject, the treatment compliance rate is estimated as follows

Compliance rate (%) =  $100 * \text{actual treatment duration} / \text{intended treatment duration}$

More specifically, the actual treatment duration will be calculated by minimum of [Day 353 date, last dose date, death date, and the first primary efficacy outcome date] - first dose date + 1 - dose interruption days. The intended treatment duration will be calculated by minimum of [Day 353 date, death date, and the first primary efficacy outcome date] - first dose date + 1 - dose interruption days due to the reasons specified in protocol 10.2.1 (for example, bleeding, and other AEs).

Compliance rate will be summarized by treatment group.

### **3.5 Duration of Exposure**

Duration of treatment exposure is defined as the duration between the first dose date and last dose date, inclusive. Note that temporary study drug interruption is not excluded from this definition. Duration of treatment exposure will be summarized by treatment group.

Number of patients who had interruptions and total interruption days will be summarized by treatment group.

### **3.6 Protocol Deviations**

Major protocol deviations will be summarized by treatment group. The categories of protocol deviations may include, but are not limited to the following:

- Not meeting key inclusion or exclusion criteria
- Taking incorrect study drug
- Not discontinuing study drug permanently according to the protocol
- Having been taking prohibited concomitant therapies as specified in the protocol

### **3.7 Prior and Concomitant Medications**

Medications received prior to the first dose of study drug are considered prior medications, even if the subject continued on the medication concomitantly with the study drug.

- The number and percentage of subjects who received prior medications will be summarized.
- The number and percentage of subjects who received any anticoagulant/antiplatelet medication taken after the Fontan procedure and prior to first dose of study drug will be summarized.

Concomitant medications include all other medications received between the first dose and the last dose of study drug.

- The number and percentage of subjects who received concomitant medications will be summarized.

Separately, anticoagulant/antiplatelet use after the study treatment period (i.e., after stopping study treatment) will be summarized.

All prior and concomitant medications will be summarized using the WHO-DD.

## **4. SAFETY**

No formal hypothesis testing will be performed.

If the date of an outcome event is missing or partially missing, the earliest logically possible date after enrollment will be used as the event date. The date of an outcome event is defined as the maximum of date of enrollment and the first day of the month if only day is missing and is defined as maximum of date of enrollment and the first day of the year if both day and month are missing. Maximum efforts will be undertaken to avoid missing event data.

All missing or partial data will be presented in the subject data listing as they are recorded on the eCRF.

Unless otherwise stated, all safety summaries and analyses will be performed based on the Safety Analysis Set (which is equivalent to Full Analysis Set).

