9.1.3. Open-label Treatment Period

9.1.3.1. Part A

There will be up to 7 planned study visits and 1 telephone contact:

- Visit 1 - Screening visit (up to 21 days prior to the first dose of study drug)
- Visit 2-D1 – Enrollment and PK and PD sampling after first dose of study drug administered on site, dispense drug supply (Day 1)
- Visit 2-D4 – PK and PD sampling before and after the Day 4 dose of rivaroxaban (Day 4)
- Visit 2-D12 – Communicate to subject if rivaroxaban treatment will be continued. Physical examination and dispense 3-month drug supply (Day 12)
- Visit 3 – Physical examination, PK, PD, and dispense 3-month drug supply (Month 3)
- Visit 4 – Physical examination, transthoracic echocardiogram, adjustment of dose (if needed), and dispense 6-month drug supply (Month 6)
- Visit 5 - Physical examination, PK, PD, transthoracic echocardiogram, lab testing, final visit (Month 12)
- Phone call – Follow-Up Contact

Approximately 10 subjects are planned to be enrolled in Part A. Subjects will receive the first dose of rivaroxaban on Visit2/Day1 (on site). Any visit may take place while the subject is hospitalized.

On Day 1 and Day 4, blood samples for PK and PD assessments will be collected by venipuncture. Ideally, an intravenous line could be placed by an experienced pediatric phlebotomist on the days of multiple blood draws. For the detailed schedule see Section 9.2, Pharmacokinetics/Pharmacodynamics Evaluations.

Pharmacokinetic and PD (PT and aPTT tests) blood samples will be sent to the central laboratory after the collection of the last sample on Day 4 (ie, after the 6.0 to 8.0 hour sample). Results are anticipated to be available for DRC review 4 to 6 days after the samples are received by the central laboratory.

An internal DRC will review the subject's PK, PD and safety data obtained from the Initial PK, PD, and Safety Assessment Period prior to allowing the subject to continue on rivaroxaban therapy to complete the 12-month period. The sponsor will notify the investigator about the DRC decision prior to Visit 2-D12 (+ 9 days). At this visit, the subject will either be informed to continue on rivaroxaban in the 12-month Open-Label Treatment Period or be discontinued from the study.

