9.1.3.2. Part B

Enrollment in Part B of this study will begin after enrollment in Part A ends. This recommendation will be made by the IDMC.

There will be up to 5 planned study visits and 2 phone contacts:

- Visit 1 – Screening visit (up to 21 days prior to the first dose of study drug)
- Visit 2 – enrollment, randomization, PK and PD sampling and first dose of study drug administration on site; dispensation of 3-month drug supply (Day 1)
- Phone call - after 12 days of the start of study drug
- Visit 3 – Physical examination, PK, PD, and dispense 3-month drug supply (Month 3)
- Visit 4 – Physical examination, transthoracic echocardiogram, adjustment of dose (if needed), and dispense 6-month drug supply (Month 6)
- Visit 5 – Physical examination, PK, PD, transthoracic echocardiogram, lab testing, final visit (Month 12)

- Phone call – Follow-Up Contact, 30 days after last study drug is taken.

Approximately 90 subjects are planned to be enrolled in Part B. Any visit may take place while the subject is hospitalized.

Subjects will be enrolled and randomized on Visit 2/Day 1 after meeting inclusion and exclusion criteria. Subjects may be enrolled and randomized on the business day prior to Day 1 to facilitate logistics provided the investigator ensures that the subject meets all eligibility criteria prior to randomization. The first dose of study drug will be administered on site on Day 1 if the subject is still eligible. Subjects will be contacted by phone at approximately 12 days (\pm 9 days) after the first dose to obtain safety and efficacy information after the start of study drug. Visits 3 and 4 are treatment visits and occur after 3 months and 6 months of therapy, respectively. Visit 5 is the end of study visit (Month 12). Transthoracic echocardiograms will be obtained at screening, at Month 6, and at the end of the study (Month 12), or ESMD visit (for details see Section 9.1.6, Transthoracic Echocardiograms). Safety and efficacy will be evaluated throughout the study.

For subjects randomized to rivaroxaban, blood samples for PK and PD evaluations will be collected. For details see Section 9.2, Pharmacokinetics/Pharmacodynamics Evaluations.

For Safety and Efficacy evaluations see Section 9.3, Safety Evaluations/Outcomes, and Section 9.4, Efficacy Evaluations/Outcomes, respectively.

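### Partial outcome-event dates are floored at enrollment, not first dose, so for some Part B children an event could be imputed out of the main summaries

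*SAP*

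**What the plan says.** **Date rule.** SAP Section 4 (Safety) gives a general principle, that "the earliest logically possible date after enrollment will be used as the event date", and then two formulas. The event date is "defined as the maximum of date of enrollment and the first day of the month if only day is missing", and it is the "maximum of date of enrollment and the first day of the year if both day and month are missing". No formula is given for a fully missing date, so the general sentence governs and points to enrollment.

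**Analysis periods.** In SAP Section 2.3 the On-Treatment Period "includes all data from the first dose of study drug to 2 days after the last dose". The Up-to-End-of-Treatment and Up-to-Last-FU Periods also open at first dose. The main bleeding description uses the On-Treatment Period (SAP Section 4.1). The main efficacy description uses the Up-to-End-of-Treatment Period (SAP Section 5).

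**Enrollment relative to dosing.** For Part B, Protocol Section 9.1.3.2 says: "Subjects may be enrolled and randomized on the business day prior to Day 1 to facilitate logistics". It also says: "The first dose of study drug will be administered on site on Day 1 if the subject is still eligible". For Part A, the Day 1 visit in Protocol Section 9.1.3.1 reads "Enrollment and PK and PD sampling after first dose of study drug administered on site", so enrollment and first dose share a date.

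**The concern.** Choosing the earliest possible date is meant to keep an event and place it conservatively. With an enrollment floor, a bleed that happened on treatment can be given a date before treatment began. Each main summary is defined by a period that opens at first dose, so the event would not be counted there. Up-to-Last-FU would not recover it, because that period opens at first dose too. No SAP rule moves a pre-dose imputed date forward, and none says how an outcome event dated between enrollment and first dose is counted.

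No hypothesis is tested and few events are expected, so the descriptive counts are the trial's comparative result. A single event is visible in arms of about 60 and 30.

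**Working it through.** The plan states no figure that depends on this rule, so there is none to reproduce. The check applies the rule as written and compares the result with first dose.

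**Inputs**
- Imputed date, day missing: max(enrollment date, first of recorded month) (SAP Section 4).
- Imputed date, day and month missing: max(enrollment date, first of recorded year) (SAP Section 4).
- Start of every analysis period: first dose (SAP Section 2.3), which in Part B is Day 1.
- Part B size: about 90, allocated 2:1 (SAP Sections 1.4 and 1.5), giving 90 × 2/3 = 60 rivaroxaban and 90 × 1/3 = 30 ASA.

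**Step 1. Worked dates** (2018 calendar for illustration; day missing, event recorded in the month of first dose)

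| Enrolled | First dose | Imputed event date | Relative to first dose |
|---|---|---|---|
| Thu 15 Mar | Fri 16 Mar | 15 Mar | 1 day before |
| Fri 16 Mar | Mon 19 Mar | 16 Mar | 3 days before |
| Fri 30 Mar | Mon 2 Apr | 1 Apr | 1 day before |
| Wed 28 Feb | Thu 1 Mar | 1 Mar | same day, inside |
| Mon 19 Mar | Mon 19 Mar | 19 Mar | same day, inside |

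If the recorded month is later than that of first dose, the first of that month is the maximum and falls after first dose, so the event is inside the period.

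**Step 2. All weekday Day 1 dates in 2018** (261 dates, public holidays ignored, enrollment always on the preceding business day). The gap is 1 day for 208 dates and 3 days for 53.
- Day missing, event in the month of first dose: the imputed date is before first dose for 253 of 261. The other 8 are Day 1 dates that are themselves the first of a month.
- Day and month missing, event in the year of first dose: before first dose for 260 of 261.
- First dose date used as the floor: before first dose for 0 of 261.

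These counts are conditional on early enrollment and on a qualifying partial date.

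**Step 3. Weight of one lost event** (exact Clopper-Pearson 95% intervals, which are an assumption because the SAP names no method)
- ASA, n = 30: 1/30 = 3.3% (0.1 to 17.2), against 0/30 = 0% (0 to 11.6).
- Part B rivaroxaban, n = 60: 1/60 = 1.7% (0.0 to 8.9), against 0/60 = 0% (0 to 6.0).
- Parts A and B rivaroxaban combined, n = 60 + 10 = 70: 1/70 = 1.4%.

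**Step 4. Knock-on in compliance.** If the rule is applied to thrombosis, SAP Section 3.4 is affected as well. Both durations there take a minimum that includes the first primary efficacy outcome date, subtract the first dose date and add 1. With no interruptions, an outcome imputed 1 day before first dose gives (−1 + 1)/(−1 + 1) = 0/0. One imputed 3 days before gives (−3 + 1)/(−3 + 1) = −2/−2, an apparent 100%.

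**The case against.** The best case for leaving the text alone has five parts.

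- **The conditions are narrow.** A reader might infer that any event with a partial date is placed on the enrollment date. The rule takes a maximum, so it does not do that. The child must be in Part B and enrolled early under an optional provision, and the date must be fully missing or partial within the month (or year) of first dose. If the first dose date itself lacks day and month, SAP Section 2.1 sets it to the randomization date; with enrollment and randomization on the same day, the conflict disappears. This stands, and it limits the point.
- **Primary events are usually well dated.** Thrombotic events rest on imaging or a clinical event and go to adjudication with a package. Major bleeding needs a hemoglobin fall, transfusion, critical site or death. Outcome events are assessed on Day 1 and at the Day 12 call, and SAP Section 4 promises strong efforts against missing event data. This stands as a reason to expect very few cases, perhaps none.
- **The event is not lost from the report.** A reader might infer that it disappears. All bleedings and any efficacy outcomes are listed, and partial dates are shown as recorded. What is lost is its place in the main incidence and Kaplan-Meier summaries.
- **The reach to efficacy is not explicit.** A reader might infer that thromboses are certainly dropped. The rule sits in the Safety section, and Section 5 has no date rule. It reaches thrombosis only through the term outcome event, which SAP Section 1.6.1 and the outcome-event footnotes to the protocol's Time and Events Schedules use for both bleeding and thrombosis. If it does not reach that far, partial thrombosis dates have no rule at all.
- **An enrollment floor fits the adjudication remit,** which covers outcomes after enrollment. An unqualified switch to first dose could move a truly pre-dose event onto treatment. This stands and shapes the fix.

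It could also be said that the earliest logical date for a known post-dose event is first dose. The formulas that follow the general sentence name enrollment, and those are what would be programmed.

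**Conclusion.** Wrong as written, low severity. The date rule and the period definitions use different starting points, and Part B allows those points to differ by one day, or three over a weekend (longer with a holiday). In that situation a post-dose event can be imputed to before first dose and left out of the main summaries, and nothing in the SAP corrects it.

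The size is one event at a time: 3.3 points for ASA and 1.7 for Part B rivaroxaban, assuming arms of about 30 and 60. These are weights per event, not an expected bias. The documents do not say how often children are enrolled early or how often event dates are partial, so no frequency can be given, and 253 of 261 must not be read as one. For bleeding the conclusion follows directly from the text. For thrombosis it depends on the broad meaning of outcome event. No test or decision rule is affected, because the trial has none.

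**What to change.** In SAP Section 4, for children who received study drug:

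- Set the imputed date to max(first dose date, first day of the recorded month), or to max(first dose date, first day of the recorded year) if the month is also missing. A fully missing date becomes the first dose date.
- Make an exception where the available information shows that the event preceded first dose. List that event separately as pre-dose. The exception is needed: for a child enrolled on Fri 30 Mar and dosed on Mon 2 Apr, an event recorded only as March is pre-dose and should not be moved to 2 April.
- State in Section 5 that the same rule applies to thrombotic events.

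The cost is a changed phrase, one exception and a cross-reference in the SAP, with the matching programming. It needs no new data and no change to trial conduct.

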## 4.1 Bleeding Events

The primary safety outcome is the major bleeding events, as defined below. Clinically relevant non-major bleeding events and trivial (minimal) bleeding will be secondary safety outcomes.

Bleeding events will be adjudicated by the CIAC using the International Society on Thrombosis and Hemostasis (ISTH) recommendations (Buller 2007, Schulman 2005).

Major bleeding is defined as overt bleeding and:

- Associated with a fall in hemoglobin of 2 g/dL or more; or
- Leading to a transfusion of the equivalent of 2 or more units of packed red blood cells or whole blood in adults; or
- Occurring in a critical site: intracranial, intraspinal, intraocular, pericardial, intra-articular, intramuscular with compartment syndrome, retroperitoneal; or
- Contributing to death.

Clinically relevant non-major bleeding is defined as overt bleeding not meeting the criteria for major bleeding but associated with:

- Medical intervention, or
- Unscheduled contact (visit or telephone call) with a physician, or
- (Temporary) cessation of study treatment, or
- Discomfort for the subject such as pain, or
- Impairment of activities of daily life (such as loss of school days or hospitalization).

Trivial (minimal) bleeding is defined as any other overt bleeding event that does not meet criteria for clinically relevant non major bleeding.

The main description will be based on Safety Analysis Set during the On-treatment period (bleeding events confirmed by the CIAC).

Incidence rates (number of subjects with bleeding event during the period divided by the number of subjects at risk at the beginning of the period) and the respective 95% CIs will be calculated for the major and clinically relevant non major bleedings by treatment group. Cumulative

incidence rates (time to first event; Kaplan-Meier) will be calculated for the major bleeding and clinically relevant non-major bleeding.

In addition, listing for all bleedings will be provided, including those that are reported more than 2 days after stop of study medication.

Baseline demographics and disease characteristics relationship to bleeding risk may be explored.

## **4.2 Adverse Events**

Treatment-emergent adverse events (TEAEs) are defined as those adverse events that occur from the first day of study drug to the last day of study drug + 2 days inclusive. Summary of the incidence of the following adverse events will be done:

- Treatment-emergent adverse events
- Treatment-emergent serious adverse events
- Serious adverse events with onset > 2 days from the stop of study drug
- Adverse events leading to permanent study drug discontinuation

In addition, incidences of adverse events by system organ class and dictionary-derived (preferred) term will be provided.

Listings will be done for all Adverse Events, and for all Serious Adverse Events.

Additional summaries, listings, or subject narratives may be provided, as appropriate.

For subjects who are not in Safety Analysis Set, AEs will be listed separately.

The ICF is signed at screening, prior to any study related procedure is done. Any AE that a subject develops after the ICF is signed but before the first dose is administered will be reported separately.

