- u) Allow at least 30 minutes from previous sample.
- v) Only PT and aPTT samples will be collected.
- w) PK, PT, aPTT, and anti-FXa assay samples will be collected.

ABBREVIATIONS

| | |
|---------------------|---|
| ACS | acute coronary syndrome |
| ALT | alanine aminotransferase |
| aPTT | activated partial thromboplastin time |
| ASA | acetylsalicylic acid |
| AST | aspartate aminotransferase |
| AUC | area under the plasma concentration time curve |
| AUC ₀₋₂₄ | area under the plasma concentration time curve from 0 to 24 hours |
| CBC | complete blood count |
| CHD | congenital heart disease |
| CIAC | Central Independent Adjudication Committee |
| C _{max} | maximum plasma concentration |
| C _{min} | minimum plasma concentration |
| CrCl | creatinine clearance |
| CRF | case report form |
| CYP3A4 | cytochrome P450 3A4 |
| D | Day |
| DRC | Data Review Committee |
| EC | Executive Committee |
| eCRF | electronic case report form |
| eDC | electronic data capture |
| eGFR | estimated glomerular filtration rate |
| ESMD | early study medication discontinuation |
| EU | European Union |
| FXa | factor Xa |
| GCP | Good Clinical Practice |
| ICF | informed consent form |
| ICH | International Conference on Harmonisation |
| IDMC | Independent Data Monitoring Committee |
| IEC | Independent Ethics Committee |
| INR | international normalized ratio |
| IRB | Institutional Review Board |
| ISTH | International Society on Thrombosis and Hemostasis |
| IWRS | interactive web response system |
| LC-MS/MS | liquid chromatography/mass spectrometry/mass spectrometry |
| LMWH | low molecular-weight heparin |
| MedDRA | Medical Dictionary for Regulatory Activities |
| NSAID | non-steroidal anti-inflammatory drug |
| NVAF | non-valvular atrial fibrillation |
| PBPK | physiologically-based pharmacokinetics |
| PD | pharmacodynamic(s) |
| P-gp | P-glycoprotein |
| PK | pharmacokinetic(s) |
| PQC | product quality complaint |
| PT | prothrombin time |
| SAP | Statistical Analysis Plan |
| SC | Steering Committee |
| SCr | serum creatinine |
| SUSAR | suspected unexpected serious adverse reaction |
| ULN | upper limit of normal |
| VKA | vitamin K antagonist |
| VTE | venous thromboembolism |

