11.4. Safety Analyses

All safety analyses will be performed on the Safety Analysis Set (described in Section 11.1.2, Analysis Sets) and by treatment group as received.

Bleeding Events

Bleeding events that occur during the On-Treatment Period will be summarized by treatment group. Bleeding events observed more than 2 days after stopping the study drug will be summarized separately. Individual listings of major and clinically relevant non-major bleeding events will be provided. The bleeding events will be adjudicated by the CIAC.

Cumulative incidences and incidence rates over time based on time to the first bleeding event will be provided by treatment group using the Kaplan-Meier method.

Adverse Events

Overall safety will also be assessed by summarizing adverse events by treatment group.

The verbatim terms used in the eCRF by investigators to identify adverse events will be coded using the Medical Dictionary for Regulatory Activities (MedDRA). Treatment-emergent adverse events are adverse events with onset during the treatment period or that are a consequence of a pre-existing condition that has worsened since baseline. All reported adverse events will be included in the analysis. For each adverse event, the percentage of subjects who experience at least 1 occurrence of the given event will be summarized by treatment group. In addition, comparisons between treatment groups will be provided if appropriate.

Individual listings of adverse events (including treatment group, age, weight, height, gender, adverse event as reported, start, duration, severity, and relationship to the study drug) will be provided. The incidence of treatment-emergent adverse events will be summarized by treatment using MedDRA preferred terms grouped by primary system organ class.

Summaries, listings, datasets, or subject narratives may be provided, as appropriate, for those subjects who die, who discontinue treatment due to an adverse event, or who experience a severe or a serious adverse event. Additional summaries, listings, or subject narratives may be provided, as appropriate.

Clinical Laboratory Tests

This study will collect laboratory data at the timepoints specified in the Time and Events Schedule. Laboratory data will be summarized by treatment group.

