12.1. Definitions

12.1.1. Adverse Event Definitions and Classifications

Adverse Event

An adverse event is any untoward medical occurrence in a clinical study subject administered a medicinal (investigational or non-investigational) product. An adverse event does not necessarily have a causal relationship with the treatment. An adverse event can therefore be any unfavorable and unintended sign (including an abnormal finding), symptom, or disease temporally associated with the use of a medicinal (investigational or non-investigational) product, whether or not related to that medicinal (investigational or non-investigational) product. (Definition per International Conference on Harmonisation [ICH])

This includes any occurrence that is new in onset or aggravated in severity or frequency from the baseline condition, or abnormal results of diagnostic procedures, including laboratory test abnormalities.

Note: The sponsor collects adverse events starting with the signing of the ICF (refer to Section 12.3.1, All Adverse Events, for time of last adverse event recording).

Serious Adverse Event

A serious adverse event based on ICH and EU Guidelines on Pharmacovigilance for Medicinal Products for Human Use is any untoward medical occurrence that at any dose:

- Results in death
- Is life-threatening
(The subject was at risk of death at the time of the event. It does not refer to an event that hypothetically might have caused death if it were more severe.)
- Requires inpatient hospitalization or prolongation of existing hospitalization
- Results in persistent or significant disability/incapacity

- Is a congenital anomaly/birth defect
- Is a suspected transmission of any infectious agent via a medicinal product
- Is Medically Important*

*Medical and scientific judgment should be exercised in deciding whether expedited reporting is also appropriate in other situations, such as important medical events that may not be immediately life threatening or result in death or hospitalization but may jeopardize the subject or may require intervention to prevent one of the other outcomes listed in the definition above. These should usually be considered serious.

For the purposes of this study, efficacy outcome events (thrombotic events) will not be reported as adverse events or serious adverse events, as they will be reported as efficacy outcomes (See Section 12.3.1, All Adverse Events.).

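### SAP 4.2 leaves the protocol's worsening clause out of the treatment-emergent definition, and its first-day start conflicts with its own pre-dose paragraph and with SAP 2.3

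*SAP*

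**What the plan says.** SAP 4.2 (Adverse Events) defines TEAEs as "those adverse events that occur from the first day of study drug to the last day of study drug + 2 days inclusive". It has no limb for worsening. The closing paragraph of the same section adds: "Any AE that a subject develops after the ICF is signed but before the first dose is administered will be reported separately".

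Protocol 11.4 (Safety Analyses) has two limbs. It counts AEs with "onset during the treatment period or that are a consequence of a pre-existing condition that has worsened since baseline". Protocol 12.1.1 says of the term adverse event: "This includes any occurrence that is new in onset or aggravated in severity or frequency from the baseline condition". It also notes: "The sponsor collects adverse events starting with the signing of the ICF".

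Two other SAP sections bear on this. SAP 2.3 opens the On-Treatment Period at the first dose, not on the first day. SAP 2.1 holds the first dose as a date and mentions no clock time. The stated rationale for SAP Amendment 1 covers protocol-deviation categories, the PK/PD section and a removed attachment. It does not mention a change to the TEAE definition.

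**The concern.** Two things are wrong with the SAP wording.

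- **Worsening.** AEs are collected from consent, screening may last up to 21 days, and the children are within 4 months of Fontan surgery. Some may start study drug with an AE still open. If such an AE worsens on drug, the protocol counts it as treatment-emergent. Under the SAP it can fall out of the TEAE summaries, depending on how it is recorded.
- **Day 1.** An AE on the day of first dose but before dosing satisfies both the TEAE definition and the pre-dose paragraph. Two programmers could classify it differently and both be following the SAP.

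The study tests no hypothesis, so the descriptive safety tables are what a reader will use. Two definitions of the same AE population, one in each document, should not both stand.

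**Working it through.** The plan gives no figure to reproduce, so the check sets the rules side by side for each kind of event.

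1. **Condition present before consent that worsens on drug.** Under Protocol 12.1.1 the aggravation is itself an AE. Recorded with an onset on drug, it is a TEAE under both documents.
2. **AE that starts between consent and first dose, worsens on drug, and has the worsening entered as a new record.** TEAE under both documents.
3. **The same AE kept as one record with its original onset.** Protocol 11.4: treatment-emergent, through the worsening limb. SAP 4.2: onset precedes the window, and the last paragraph sends the event to separate reporting. The documents disagree.
4. **AE on Day 1 known to precede the dose.** SAP 4.2 definition: TEAE. SAP 4.2 last paragraph: reported separately. SAP 2.3: outside the On-Treatment Period. The SAP disagrees with itself.
5. **AE on Day 1 with unknown time.** The definition counts it. The SAP gives no rule for deciding whether the pre-dose paragraph applies.

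Case 3 is possible because the documents do not say how worsening is recorded. Footnote m (Part A) and footnote n (Part B) of the Time and Events Schedules have visits review both ongoing and new AEs. The Protocol 11.4 listing carries start, duration and severity. Both are compatible with one running record per event. The SAP definition uses the verb occur without saying whether onset is meant, although one of the summaries listed under it is worded by onset.

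**Largest effect per child (Part B).** Inputs: about 90 children randomised 2:1 (Protocol 3.1, SAP 1.5).

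- Rivaroxaban: 90 × 2/3 = 60, so one child is 1/60 = 1.7 points.
- ASA: 90 × 1/3 = 30, so one child is 1/30 = 3.3 points.

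Protocol 11.4 counts subjects with at least one occurrence. These are therefore maxima: the overall TEAE percentage moves only if the child has no other TEAE.

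**Length of the Day 1 overlap.** Taking 12 months as 365 days (an assumption), the window is 365 + 2 = 367 days. The pre-dose part of Day 1 is less than 1/367 = 0.27% of it. This is a share of time, not of events, and the documents give no AE rate for Day 1.

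**The case against.** The case against acting is that the documents already limit the damage. The pre-dose paragraph is the more specific rule and can be read as overriding the general window. Protocol 12.1.1 makes an aggravation an AE in its own right, so most worsening is captured. All AEs and all serious AEs are listed. The primary safety outcome, adjudicated major bleeding, is described on the On-Treatment Period, which starts at first dose. Programming instructions are in the Data Presentation Specifications, which are not among the documents and may settle the matter.

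Most of this stands, and it is why the point is minor. It does not remove case 3, and it does not tell a reader of the SAP which Day 1 rule prevails.

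Three stronger readings are tempting, and the documents do not support them.

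- **That Day 1 pre-dose events are simply counted as on-drug.** The pre-dose paragraph says otherwise. The defect is a conflict between two rules.
- **That conditions worsening on drug are lost in general.** Only case 3 is at risk.
- **That the rule biases the rivaroxaban arm, because only those children have a blood draw before the first dose.** The Part B schedule places that draw under a rivaroxaban-only heading, and Protocol 9.2 agrees. Footnote v ("Only PT and aPTT samples will be collected") says nothing about arm. Footnote b of the same schedule and Protocol 9.1.2 describe Day 1 pre-dose PT and aPTT testing in Part B with no arm limit. The one-arm premise is therefore not established. Rivaroxaban children also have two post-dose draws on Day 1, so redefining TEAEs would not remove a difference in sampling.

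**Conclusion.** The point holds as a minor discrepancy. The SAP drops a limb of the protocol's TEAE definition without explanation, and its start rule conflicts with its own pre-dose paragraph and with SAP 2.3. The effect is confined to the TEAE summaries, up to the per-child maxima shown above. The number of affected children is not given and is probably small.

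This rests on three assumptions: that some pre-dose AEs that worsen are kept as single records, that the Data Presentation Specifications do not already resolve the two rules, and that Part B enrols about 60 and 30 children.

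**What to change.** Replace the definition in SAP 4.2 with wording to this effect: a TEAE is an AE with onset at or after first dose through last dose + 2 days, or a pre-existing condition or pre-dose AE that worsens from baseline in severity or frequency (the terms of Protocol 12.1.1) within that window. Count Day 1 AEs as TEAEs unless they are recorded as pre-dose. Keep the separate pre-dose report for AEs that do not meet this definition. State in the SAP or the eCRF completion guidelines how worsening of a pre-dose AE is recorded, because it can be flagged only if the data show it.

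The cost is a short SAP edit and a flag in the AE dataset. The documents do not show a clock time or a pre/post-dose field for AEs. The Day 1 default works without one, but a known pre-dose event can be taken out only if its timing is captured.
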